7.1.1 Molecular pre-screening

Local pre-screen

If local testing will be conducted to determine the molecular status of the tumor, potential patients will be asked to sign a “Pre-screening Informed Consent” to allow for the collection and analysis of the sample.

A consent form is not needed if the molecular status of the tumor was previously determined. Evidence of local data must be present in the source documentation.

7.1.2 Clinical Screening

The IRB/IEC study approved informed consent form (ICF) must be signed and dated before any screening procedure is performed. Procedures which are part of the clinical routine during the initial diagnostic work-up of the patient may be obtained before obtaining the ICF. A copy of the ICF must be given to the patient or to the person signing the form. The investigator or designee must record the date when the study informed consent was signed in the medical records of the patient.

Patients will be evaluated against study inclusion and exclusion criteria and safety assessments. For details of assessments, refer to [Table 7-1](#). Screening assessments must be completed within 28 days prior to the first dose of treatment with the exception of the serum pregnancy test (β -hCG) that needs to be performed ≤ 72 hrs before the first dose of study treatment. Clinical and radiological tumor assessment (RANO criteria) should be conducted preferably within 1 week (7 days) prior to the first dose of the study drug; however tumor assessments up to 4 weeks (28 days) prior to the first dose will be acceptable. Screening assessments must be repeated if >28 days from Cycle 1 Day 1.

7.1.2.1 Enrollment process

After the patient has signed an ICF to participate in the treatment phase of the study, an enrollment form detailing the patient's age, gender, disease type, screening date, and required genetic alteration, as well as the anticipated date of first study drug treatment. The enrollment form will be faxed or e-mailed to the Novartis Clinical Trial Lead or his/her designee for approval and acknowledgement of patient inclusion.

7.1.2.2 Information to be collected on screening failures

Patient who

- signed a molecular pre-screening ICF but are considered as ineligible after molecular screening
- are found not eligible to participate in the treatment phase of the study, after signing the informed consent form
- are not started on study treatment based on the opinion of the investigator
- withdraw consent prior to initiating study drug

will be considered as screening failures, and data will be handled in the same manner. The molecular pre-screening failure or screening failure will be entered on the Screening Phase Disposition Page. The demographic information, informed consent, and Inclusion/Exclusion pages must also be completed for Screen Failure subjects. No other data will be entered in the database for patients who are screen failures, unless the patient experienced a Serious Adverse Event during the screening phase (see [Section 8](#) for SAE reporting details).

The following data must be collected in the source documents for any patient who signs an ICF:

- Informed consent information
- Inclusion/exclusion
- demography
- Screening log page (including reason for not being started on treatment)
- Serious Adverse Event (see [Section 8](#) for SAE collection, requirements and reporting)

7.1.2.3 Patient demographics and other baseline characteristics

Data to be collected will include general patient demographics, relevant medical history and current medical conditions, prior concomitant medications, diagnosis and extent of tumor, baseline tumor mutation status (gene amplification or translocation) and details on prior antineoplastic treatments.

7.1.3 Treatment period

During the treatment period, the patient is obliged to follow the investigators instructions with regards to contraception, concomitant medications and dosing regimen. There is no fixed duration; patients may continue treatment with the study drug until the development of an unacceptable toxicity that precludes any further treatment, disease progression, and /or treatment is discontinued at the discretion of the Investigator or by patient refusal.

For the patients included in group 2 (surgical group), there is a fixed treatment duration of 5 to 10 days before surgery. The last dose should be on the day of surgery, or the day before at the discretion of the investigator. At a minimum of 2 weeks post-surgery, patients may resume study treatment with BGJ398 until experiencing unacceptable toxicity, disease progression and/or the treatment is discontinued at the discretion of the investigator or by patient refusal (withdrawal of consent). Day 1 of treatment following surgery will be considered to be Cycle 1 Day 1. For details of assessments during the treatment period, refer to [Table 7-1](#).

7.1.4 End of treatment visit including study completion and premature withdrawal

At the time patients discontinue study treatment, a visit should be scheduled within 14 days, at which time all of the assessments listed for the End of Treatment (EOT) visit will be performed. An **End of Treatment Phase Disposition** CRF page should be completed, giving the date and reason for stopping the study treatment.

At a minimum, all patients who discontinue study treatment, including those who refuse to return for a final visit, will be contacted to return 30 days after the last administration of the study treatment.

In addition, patients who discontinue study treatment for any reasons other than disease progression, death, or withdrawal of study consent, should also return for disease follow-up and will be followed for survival (please refer to [Section 7.1.5](#)) and should not be considered withdrawn from the study. If patients refuse to return for these visits or are unable to do so, every effort should be made to contact them or a knowledgeable informant by telephone to obtain the follow-up information.

If a patient discontinues study treatment, but continues study assessments in the follow-up period, the patient remains on study until such time as he/she completes protocol criteria for ending study assessments. At that time, the reason for study completion should be recorded on the **Study Phase Completion Disposition** CRF page.

7.1.4.1 Criteria for premature patient withdrawal

Patients may voluntarily withdraw from the study or be dropped from it at the discretion of the investigator at any time. Patients may be withdrawn from the study if any of the following occur:

- Unacceptable AE(s)
- Delay in dosing > 14 consecutive days (unless agreed otherwise between Novartis and the Investigator).
- Pregnancy of the patient
- Patient withdrew consent
- Lost to follow-up
- Disease progression (clinical or radiological)
- Initiation of new cancer therapy

Note: refer to [Section 7.1.5](#) for the requirement to further follow patients after discontinuation of study treatment.

7.1.4.2 Replacement policy

No replacement will be needed.

7.1.5 Follow up period

Patients lost to follow up should be recorded as such on the eCRF. For patients who are lost to follow-up, the Investigator should show "due diligence" by documenting in the source documents steps taken to contact the patient, e.g., dates of telephone calls, registered letters, etc.

30-day safety follow-up period

All patients must complete the safety follow-up assessments 30 days after the last dose of the study treatment.

All AEs suspected to be related to study drug should be followed up weekly, or as clinically indicated, until resolution or stability (see also [Section 6.2.2](#)).

Disease progression follow-up period

All patients enrolled in the study who discontinue study treatment for any reason other than disease progression will be followed up monthly via a phone call and will have MRI scan (or CT if the patient cannot tolerate MRI) every 8 weeks (± 7 days) as detailed in [Table 7-1](#), until disease progression or the initiation of subsequent anticancer therapies, or death, whichever occurs first.

Survival follow-up period

All patients enrolled in the study will be followed for survival every 4 months for at least one year per e.g., phone call, after LPLT. Possible newly started antineoplastic therapies during this FU period must be recorded on the Antineoplastic therapy since discontinuation eCRF.

7.2 Assessment types

7.2.1 Efficacy assessments

Tumor response and progression will be assessed by the Investigator, using the Response Assessment in Neuro-Oncology (RANO) Working Group ([Wen et al. 2010](#)) as detailed in [Appendix 3](#).

Each patient will be evaluated for all potential sites of tumor lesions at Screening and every 8 weeks after starting study treatment until disease progression.

On-study tumor assessments have a ± 7 day window, except for the first post-baseline tumor assessment and for confirmatory scans (4 weeks +7 day window only). The first post-baseline tumor assessment should be performed on day 1 of cycle 3 (+7 day window permitted) after starting treatment. There will be a tumor assessment at the End of Treatment (+ 7 days) if the patient discontinues for any reason other than disease progression and the last tumor assessment has been performed > 28 days prior to this day.

For group 1, the baseline scan must occur within 28 days of treatment initiation. For group 2, patients undergoing surgery, per standard of care, a MRI should be performed within 72 hours after surgery ([Wen et al. 2010](#)). This scan can function as the baseline scan if BGJ398 therapy is initiated within four weeks of surgery. If BGJ398 is initiated after 4 weeks following surgery, a baseline scan must be performed within 7 days of starting BGJ398. Subsequent post baseline scans will be performed as described above. For group 2 patients who do not undergo surgery the baseline scan will be defined as per group 1.

Note: in case a patient cannot tolerate MRI, the patient may still participate in the study following discussion between Novartis and the investigator. In this case, all efficacy assessments will be made by CT scans for that patient. Efficacy assessments should be performed by using the same technique throughout the study for each patient.

7.2.2 Safety and tolerability assessments

Safety will be monitored by assessing the procedures listed below as well as collecting of the adverse events at every visit. For details on AE collection and reporting, refer to [Section 8](#).

7.2.2.1 Physical examination

A complete physical examination must be performed as indicated in [Table 7-1](#).

Physical examination will be performed on the scheduled day, even if study treatment is being withheld. More frequent examinations may be performed at the discretion of the Investigator and if medically indicated.

Physical examination will be performed according to the standards at each institution.

Information about the physical examination must be present in source documentation at the study site. Significant findings that are present prior to signing of informed consent form for the study must be included in the Relevant Medical History/Current Medical Conditions page on the patient's eCRF. Significant new findings that begin or worsen after informed consent for the study must be recorded on the AE eCRF.

7.2.2.2 Vital signs

Vital signs (body temperature, pulse rate, blood pressure) must be performed before dosing and as indicated in [Table 7-1](#).

Vital signs should be assessed on the scheduled day, even if study treatment is being withheld. More frequent examinations may be performed at the discretion of the Investigator and if medically indicated.

7.2.2.3 Height and weight

Height and body weight will be measured. Weight will be measured as indicated in [Table 7-1](#). Height will be collected at screening only. More frequent examinations may be performed at the discretion of the Investigator and if medically indicated.

7.2.2.4 Performance status

The ECOG performance status (please refer to [Table 7-2](#)) will be assessed as indicated in [Table 7-1](#). Assessment via Karnofsky Performance Scale is acceptable but requires subsequent conversion to ECOG ([Ma et al, 2010](#)) before being reported on the e-CRF. Assessments of performance status will be performed on the scheduled day, even if study treatment is being withheld.

Table 7-2 ECOG performance status

Grade	ECOG Status
0	Fully active, able to carry on all pre-disease performance without restriction
1	Restricted in physically strenuous activity but ambulatory and able to carry out work of a light or sedentary nature (e.g., light house work, office work)
2	Ambulatory and capable of all self-care but unable to carry out any work activities. Up and about more than 50% of waking hours
3	Capable of only limited self-care, confined to bed or chair more than 50% of waking hours
4	Completely disabled. Cannot carry on any self-care. Totally confined to bed or chair

Note: Grade 5 (dead) was removed from this table. This information will be collected on a separate eCRF page.

7.2.2.5 Laboratory evaluations

Clinical laboratory analyses are to be performed by the local laboratory as indicated in [Table 7-1](#) and [Table 7-3](#). Laboratory tests will be collected and analyzed on the scheduled day, even if study treatment is being withheld. More frequent assessments may be performed at the discretion of the Investigator and if medically indicated, and should be recorded on the Unscheduled Visit eCRFs.

At any time during the study, abnormal laboratory parameters which are clinically relevant (e.g., require dose modification and/or interruption of study treatment, lead to clinical symptoms or signs, or require therapeutic intervention), whether specifically requested in the protocol or not, will be recorded on the Adverse Events eCRF page. Laboratory data will be summarized using the CTCAE (version 4.03).

Novartis must be provided with a copy of the laboratory's certification, and normal ranges for each parameter measured. In addition, if at any time a patient has laboratory parameters

obtained from a different outside laboratory, Novartis must be provided with a copy of the certification and normal ranges for that laboratory.

Table 7-3 Clinical laboratory parameters collection plan

Test Category	Test Name
Hematology	Hematocrit, Hemoglobin, Platelets, White blood cells, Differential (Basophils, Eosinophils, Lymphocytes, Monocytes, Neutrophils)
Biochemistry	Albumin, Alkaline phosphatase, ALT (SGPT), AST (SGOT), Calcium (Total), Chloride, Creatinine, Blood Urea Nitrogen (BUN) or Urea, Potassium, Sodium, Magnesium, Inorganic Phosphorous . Direct Bilirubin, Indirect Bilirubin, Total Bilirubin, direct/indirect bilirubin, Total Protein, Uric Acid, Amylase, Lipase.
Urinalysis	Macroscopic Panel (Dipstick) (Blood, Glucose, Ketones, pH, Protein, Specific Gravity). Microscopic Panel (Red Blood Cells, WBC).
Coagulation	Prothrombin time (PT) or International normalized ratio [INR]), Partial thromboplastin time (PTT),
Pregnancy Test	Serum hCG at screening; EOT and other times points serum hCG or urine.

7.2.2.5.1 Hematology

Hematology tests are to be performed by the local laboratory according to the Visit Schedules outlined in [Table 7-1](#) and [Table 7-3](#).

7.2.2.5.2 Clinical chemistry

Clinical chemistry tests are to be performed by the local laboratory according to the Visit Schedule outlined in [Table 7-1](#). For details on the Biochemistry panel refer to [Table 7-3](#). Assessment of inorganic phosphorus will be performed as part of the chemistry analysis, or as indicated in [Table 7-1](#).

- On Cycle 1, Day 1, 8 hours post dose, inorganic phosphorous will be the only test conducted of the chemistry panel.
- On Cycle 1, Day 2, inorganic phosphorous will be the only test conducted of the chemistry panel.

7.2.2.5.3 Coagulation

International normalized INR, pro-thrombin time (PT), partial thromboplastin time will be measured according to the visit schedule in [Table 7-1](#) and [Table 7-3](#).

7.2.2.5.4 Urinalysis

Dipstick Urinalysis will be conducted as directed in [Table 7-3](#) on the days outlined in [Table 7-1](#) or as clinically indicated, within the windows outlined in [Section 7.1](#). Any significant findings on dipstick will be followed up with a microscopic evaluation (listed in [Table 7-3](#)) where WBC and RBC sediments will also be measured.

7.2.2.5.5 Pregnancy and assessments of fertility

All women of childbearing potential (pre-menopausal or less than 1 year after the onset of menopause) must have a serum pregnancy test (β -hCG) \leq 72 hrs before the first dose of study treatment. Additionally, a serum or urine pregnancy test should be performed at Day 1 of each cycle and at the End of Treatment visit.

A positive pregnancy test requires immediate interruption of study drug treatment until serum β -hCG is performed and found to be negative. If positive, the patient must be discontinued from the study. See [Section 8.4](#) for pregnancy reporting.

7.2.2.6 Radiological examinations

7.2.2.6.1 MRI scan (or CT if patient is unable to undergo MRI).

Please refer to details in [Section 7.2.1](#) and [Appendix 3](#). The same modality (MRI/CT) must be used throughout the study

First post baseline scan occurs cycle 3 day 1; subsequent scans occur every 8 weeks until unacceptable toxicity or disease progression, whichever occurs first.

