All patients must be followed up for safety assessments during 30 days after the last dose of the study treatment.

Disease progression follow-up period

All patients enrolled in the study who discontinue study treatment for any reason other than disease progression will be followed up monthly via a phone call and will have MRI scan every 8 weeks, until disease progression or the initiation of subsequent anticancer therapies, or death, whichever occurs first.

Survival follow-up period

All patients enrolled in the study will be followed e.g., phone call for survival every 4 months for at least one year per e.g., phone call per, after last patient last treatment (LPLT).

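### Two places in the protocol end tumour scans at unacceptable toxicity while five others have no such stop, so disease follow-up after a toxicity stop needs reconciling for PFS6

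*Protocol*

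**What the plan says.** Two places set a toxicity stop. Section 7.2.2.6.1 says that, after the Cycle 3 Day 1 scan, "subsequent scans occur every 8 weeks until unacceptable toxicity or disease progression, whichever occurs first". The tumour-response row of Table 7-1 has the same words in its treatment-phase cell.

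Five places have no such stop:
- Section 4.1 says that patients who come off drug without progression "will have MRI scan every 8 weeks, until disease progression or the initiation of subsequent anticancer therapies, or death, whichever occurs first".
- Section 7.1.5 covers the same group ("All patients enrolled in the study who discontinue study treatment for any reason other than disease progression will be followed up monthly") and prescribes an "MRI scan (or CT if the patient cannot tolerate MRI) every 8 weeks" with the same three end points, pointing to Table 7-1 for detail.
- Section 7.1.4 sends these patients to disease follow-up and says they "should not be considered withdrawn from the study".
- Section 7.2.1 and Appendix 3 run 8-weekly assessment to progression. Section 7.2.1 adds an end-of-treatment scan if the last one is more than 28 days old. SAP 2.7 repeats 7.2.1.

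A second group of texts concerns leaving the study. Section 7.1.4.1 opens with "Patients may be withdrawn from the study if any of the following occur", and its list includes unacceptable adverse events and a dosing delay beyond 14 days. In Table 6-3, the rows for QTcF prolongation, hypercalcaemia and vomiting take the patient off the study, where most other rows say study treatment. The design paragraph of 4.1, repeated in SAP 1.1, runs scans only until progression or until the patient leaves the study.

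**The concern.** PFS6 needs progression status out to 6 months whether or not the patient is still on drug. If toxicity ends the scans, a patient who stops early without progression has no later radiological status. The leaving-the-study wording opens a second route to the same result: a site could record a toxicity patient as off study and, under the design paragraph of 4.1, stop scanning.

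Two things may then happen in the primary analysis. The patient may be censored at the last scan (protocol 10.4.3, SAP 2.5.3). Or, with no scan later than 8 weeks and no earlier progression, the patient falls outside the per-protocol set (PPS; protocol 10.1.3, SAP 2.2), on which the primary analysis rests. Sites could also differ in what they do. With 24 patients planned in the PPS, a few such cases matter.

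**Working it through.** **Which scans are affected.** Cycle 3 Day 1 is study day 2 × 28 + 1 = 57. Later scans fall on days 57 + 56 = 113 and 113 + 56 = 169. By the SAP month length, 6 months is 6 × 30.4375 = 182.6 days. So three scheduled scans inform PFS6.

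**Two illustrative patients, neither with progression.**

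| | Last dose day 70 | Last dose day 30 |
|---|---|---|
| Scans to date | Day 57 | None after baseline |
| End-of-treatment scan (7.2.1) | Not required: visit by day 70 + 14 = 84, and 84 − 57 = 27 days | Required: by day 30 + 14 + 7 = 51 |
| Literal 7.2.2.6.1 | Days 113 and 169 not done | No scan after day 51 |
| Sections 4.1 and 7.1.5 | Days 113 and 169 done, unless new therapy or death comes first | 8-weekly scans go on, with the same exceptions |
| Consequence of the literal text | May be censored at day 57 | No scan beyond 8 weeks (day 57), so outside the PPS |

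**How the analysis treats them.** Sections 10.4.3 and SAP 2.5.3 censor at the last tumour assessment when a patient leaves the study and is lost. Appendix 3 (14.3.5.3) also allows censoring once regular assessments are no longer available. Deaths count as PFS events and survival follow-up covers everyone, so not every later event is lost.

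**Direction.** The primary analysis is a Weibull time-to-event model. It can use a censored time, but it assumes that patients censored at a toxicity stop carry the same later risk as those still observed. If risk is higher after stopping, PFS6 is overestimated; if lower, underestimated. Exclusion from the PPS has no fixed direction, because it depends on the outcomes of those excluded.

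**Reproducing the plan's figure.** I simulated the protocol 10.4.2 to 10.8 design: stated priors with time in months, 24 patients, one per month, interim at 10, 1000 trials per scenario. The true Weibull shape is not stated; I took 1.
- Prior check: P(PFS6 < 16%) = 64.9% and P(PFS6 > 40%) = 25.8%, against the stated 65% and 25%.
- Success at a true PFS6 of 50%: 84.8%, against 86.1% in Table 10-2. The Monte Carlo standard error is about √(0.861 × 0.139/1000) = 1.1 points.
- Not matched as closely: mean events 19.5 against about 17, and interim stopping at a true 16% of 79.2% against 81.6%.

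**How many statuses could be lost.** Let p be the true PFS6 and q the chance of a toxicity stop by 6 months if progression did not intervene. The documents give no q; 10%, 20% and 30% are assumptions. With constant hazards, and scans ending at the stop for every patient, the share without an observed 6-month status is

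ln(1 − q) / [ln p + ln(1 − q)] × [1 − p(1 − q)].

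At p = 0.50:
- q = 0.10: 0.1054/0.7985 × 0.55 = 7.3%
- q = 0.20: 0.2231/0.9163 × 0.60 = 14.6%
- q = 0.30: 0.3567/1.0498 × 0.65 = 22.1%

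The simulation gives 7.0%, 14.6% and 21.7% in trials that reach the final analysis. In 24 patients, 7.3% is about 1.8 and 22.1% about 5.3.

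**Effect on success when censoring is independent of risk.**

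| True PFS6 | Scans continue | q = 0.10 | q = 0.20 | q = 0.30 |
|---|---|---|---|---|
| 50% | 84.8% | 83.3% | 83.9% | 80.2% |
| 40% | 44.1% | 44.2% | 45.8% | 47.7% |
| 16% | 0.0% | 0.1% | 0.0% | 0.0% |

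The changes are small and several are within simulation error. This run cannot detect bias from informative censoring, because it assumes there is none, and it drops nobody from the PPS.

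**The case against.** The strongest reply is that the protocol, read as a whole, already keeps these patients in follow-up. Much of it stands.
- The toxicity wording in Table 7-1 sits in the treatment-phase block, and toxicity is one of the events that ends treatment, so the cell may describe on-treatment scanning only. The row has two further X marks. I could not confirm their exact columns, but both fall after the treatment phase. A reader might infer that the table as a whole ends scanning at toxicity; those marks, and the pointer from 7.1.5, do not support that.
- Section 7.2.2.6.1 itself opens with "Please refer to details in" and names 7.2.1 and Appendix 3, neither of which has a toxicity stop.
- Section 7.1.4.1 closes with a note sending the reader to 7.1.5 for further follow-up. The glossary entry on premature withdrawal also leaves room for following a withdrawn patient for progression or survival.

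Status is therefore lost only where a site acts on the narrower text. What the reply does not remove is that 7.2.2.6.1 states a stop outright, that 7.1.5 refers for its scans to a table containing the same stop, and that leaving the study is used for toxicity in Table 6-3 while 4.1 makes it an end point for scanning.

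**Conclusion.** This is an internal inconsistency in wording, not a flaw in the intended design, which 4.1 and 7.1.5 make clear. It should be corrected because a stated rule, followed literally, would lose post-toxicity progression data for the primary endpoint.

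A reader might infer that PFS6 will be overstated, and by several points near the 40% threshold. The documents do not support that. They give no rate of stopping for toxicity before 6 months in this trial and no risk of progression after stopping, and PPS exclusion could act either way. The phase I figures in 1.2.1.2.1 are for adverse events, interruptions and reductions, not permanent stops. The supportable statement is that censoring may become informative, with size and direction unknown.

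The 7% to 22% range for missing 6-month status is an illustration. It rests on assumed stop rates, constant hazards, a true PFS6 of 50% and every site following the literal text, which makes it an upper case for those rates.

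**What to change.** In 7.2.2.6.1 and the Table 7-1 tumour-response cell, replace the toxicity stop with the 7.1.5 end points: every 8 weeks, on or off drug, until progression, subsequent anticancer therapy or death. Reconcile 7.1.4.1, and the Table 6-3 rows that take a patient off the study, with 7.1.4 and 7.1.5, so that it is plain whether the patient stays in disease follow-up. When treatment stops is not altered.

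The cost is wording in a protocol amendment. It adds no scans beyond those 4.1 and 7.1.5 already require. It does not address loss of status after new anticancer therapy, which both sections already treat as an end point. If patients have already been followed under the present text, a listing of those whose scans ended at a toxicity stop without progression would show how many are affected.
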